2.4.5.2 Secondary Outcome Measures

Secondary outcome measures include:

1. Change in spontaneous pain intensity (measured on 0-10 NRS) from baseline to 60-120 minutes after ondansetron IV infusion, compared between two sessions with and without tariquidar. The pain severity values obtained at 60, 90, and 120 minutes will be averaged to derive the secondary outcome measure. The values will be compared via paired t-test (or Wilcoxon signed-rank test, if data not normally distributed).
2. Changes in NPSI total score and sub-scores (burning pain, paroxysmal pain, paresthesia/dysesthesia score) will be compared between treatment sessions;
3. The association between baseline Conditioned Pain Modulation (CPM) magnitude (Δ CPM) and the % pain reduction from baseline will be determined by bivariate regression. A significant association between the two measures will be indicative of differential analgesic response as a function of descending pain modulation;

Exploratory analyses will be performed to determine if variables such as sex, weight, baseline wind-up ratio (WUR), peak ondansetron plasma concentration, and P-glycoprotein genotype affect the difference in pain reduction between the two study sessions.

A population PK approach will be used to model CSF concentrations of ondansetron with and without tariquidar co-administration.

Table 1. Study Day Timeline

	Drug	Blood*		PK		NRS	NPSI	CPM	WUR	QST	Questionnaires
Screening	TQD	OND	X	Blood	CSF	X	X	X	X	X	X
Study day (min after ondansetron infusion start)											
Baseline			X	X		X	X	X	X	X	
-30 min	TQD / placebo Infusion										
0 min		OND infusion		X		X					
10 min						X					
15 min				X							
20 min						X					
30 min				X	X**	X					
40 min						X					
50 min						X					
60 min				X		X					
70 min							X				
75 min						X					
90 min				X		X					
105 min						X		X	X		
120 min				X		X					
135 min						X					

150 min						X					
165 min						X					
180 min				X		X					
240 min				X		X					
Hourly after discharge- study day						X					
Post-study day (weeks)											
1						daily					
2						daily					
3			X			daily					

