2.4.7 Statistical Methods

All demographic, sensory, analytical and patient-reported data will be captured on case report forms, manually entered to a Research Electronic Data Capture (REDCap) database that will be created for the project, and will be verified by an independent study team member. Plasma and CSF concentrations of ondansetron will be analyzed using a previously validated liquid chromatography method.³⁹ Non-compartmental PK analysis will be performed to construct the concentration-time curves of ondansetron in human plasma with and without tariquidar.³¹ Ondansetron concentration in CSF will be used to evaluate biodistribution of ondansetron to CNS, by the means of CSF to plasma concentration ratio. We do not expect missing outcomes data as all primary and most secondary outcomes will be collected with the participants physically present with the research team. Any missing data will be described, but no data imputation will be attempted. Intergroup comparisons for parametric data will be performed by paired t-test, and for non-parametric data by Wilcoxon signed-rank test for paired samples. McNemar's test will be used to compare paired nominal data, and Fisher's exact test to compare non-paired nominal data.

Sample size:

Change in spontaneous pain reduction (secondary outcome) was used to determine the sample size for the study. The baseline pain intensity (\pm SD) of patients with peripheral neuropathy we have recruited to various studies over the past two years have been 6.3 ± 2.1 . This proof of concept study expects to demonstrate a 30% difference in pain reduction between the two intervention sessions. Given that in a published study of IV ondansetron in NeuP a 20% pain reduction has been observed (although not different from placebo), we assume pain intensity of 5.1 ± 2.1 in ondansetron+placebo group, and expect pain intensity of 4.0 ± 2.1 in ondansetron+tariquidar group at the 60-120 minute timeframe. To determine a significant difference with two-tailed $\alpha < 0.05$ and 85% power (effect size 0.52), 28 subjects will be required in this cross-over study. We expect to enroll 28-32 participants to the study to reach 28 evaluable participants.

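### The stated 85% power rests on the across-patient SD of baseline pain, not the SD of the within-patient difference that the planned paired test uses, so it is unsupported and could be too high or too low

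*Combined protocol and SAP*

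**What the plan says.** Section 2.4.7 (Statistical Methods, Sample size) names the outcome used for sizing: "Change in spontaneous pain reduction (secondary outcome) was used to determine the sample size for the study". It reports that baseline pain in "patients with peripheral neuropathy we have recruited to various studies over the past two years have been 6.3 ± 2.1". It then carries the same SD into both sessions: "we assume pain intensity of 5.1 ± 2.1 in ondansetron+placebo group", and 4.0 with SD 2.1 with tariquidar. The conclusion, for a two-tailed 0.05 test, is "85% power (effect size 0.52), 28 subjects will be required in this cross-over study".

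Section 2.4.5.2 defines the outcome as "Change in spontaneous pain intensity (measured on 0-10 NRS) from baseline to 60-120 minutes after ondansetron IV infusion, compared between two sessions"; one session includes tariquidar and the other does not. On the post-dose value it says: "The pain severity values obtained at 60, 90, and 120 minutes will be averaged to derive the secondary outcome measure". On the test it says: "The values will be compared via paired t-test (or Wilcoxon signed-rank test, if data not normally distributed". The synopsis gives the same definition and test.

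Neither section, nor any other part of the document, gives an SD of change, an SD of the between-session difference, or a within-patient correlation.

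**The concern.** A paired t-test works on one number per patient, here the change from baseline in one session minus the change in the other. Its power is set by the mean of that number divided by its SD across patients. The printed effect size divides by a different quantity, the spread of pain levels between patients. Section 2.4.4 says that the crossover was chosen to reduce the influence of differences between patients, yet the denominator is a measure of exactly those differences. The two SDs can agree, but only under particular correlations, and none is stated.

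At stake is whether the 85% describes the planned test. Pain is a secondary outcome (the primary objectives are pharmacokinetics and tolerability), but this calculation is the protocol's only justification for 28 patients.

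**Working it through.** **Inputs from the documents.** Means at 60-120 minutes of 5.1 and 4.0, SD 2.1 in each session, two-tailed 0.05, 28 evaluable patients, stated effect size 0.52, stated power 85% (all section 2.4.7); paired t-test on change from baseline (section 2.4.5.2). All correlations below are assumptions.

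**Step 1: the effect size.** (5.1 − 4.0)/2.1 = 1.1/2.1 = 0.524, printed as 0.52. The denominator is the across-patient SD.

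**Step 2: the stated power.** With d as the paired effect size, power comes from the noncentral t distribution with 27 degrees of freedom and noncentrality d√28. For d = 0.52 the noncentrality is 2.75 and the two-sided critical value is 2.05.
- Two-sided 0.05: power 75.6% (76.2% with d = 0.524). For 85%, 36 patients are needed (35 with d = 0.524).
- One-sided 0.05: power 85.0%, which matches the stated figure but not the stated two-tailed test.

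So the drop from 85% to 76% at an SD of 2.1 arises from the number of tails. It is a separate matter from the choice of SD.

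**Step 3: the SD that 85% requires.** Two-sided, 28 pairs, 85% power needs d of about 0.587, so the SD of the difference must be at most about 1.1/0.587 = 1.87.

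**Step 4: post-dose pain compared directly.** SD of the difference = 2.1 × √[2(1 − r)], where r is the between-session correlation. This equals 2.1 only at r = 0.5.

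| r | SD of difference | Two-sided power, n = 28 |
|---|---|---|
| 0.3 | 2.48 | 62% |
| 0.5 | 2.10 | 76% |
| 0.6 | 1.88 | 85% |
| 0.7 | 1.63 | 93% |

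**Step 5: change from baseline, the planned outcome.** Let every rating have SD 2.1, let rw be the correlation between baseline and post-dose pain within a session, and let rd be the correlation between the two sessions' changes. The variance of one change is 2 × 2.1² × (1 − rw). The variance of the difference between the two changes is 4 × 2.1² × (1 − rw)(1 − rd).

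| rw | SD, rd = 0 | Power, rd = 0 | SD, rd = 0.3 | Power, rd = 0.3 |
|---|---|---|---|---|
| 0.5 | 2.97 | 47% | 2.48 | 62% |
| 0.7 | 2.30 | 68% | 1.92 | 83% |
| 0.75 | 2.10 | 76% | 1.76 | 89% |
| 0.8 | 1.88 | 85% | 1.57 | 95% |

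The SD equals 2.1 wherever (1 − rw)(1 − rd) = 0.25, which is a curve of value pairs and not a single point. Power reaches 85% where that product is at most (1.87/2.1)²/4, about 0.20.

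**The case against.** The strongest reply is that a correlation may have been used and not printed, with 0.52 reported only as a descriptive standardised difference. That is possible. A between-session correlation of about 0.60 for post-dose pain gives 85% two-sided with 28 patients, and so does rw of about 0.80 with rd = 0 for change scores. The stated power is therefore unverifiable rather than disproved. But no correlation appears, and the effect size printed beside the 85% is not the roughly 0.59 that a paired test would need.

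The rd = 0 column should also not be read as the expected case. It supposes that a patient's response in one session says nothing about the response in the other, although both sessions include ondansetron. For non-negative rd it is the least favourable case, which is why the rd = 0.3 column stands beside it.

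Several stronger readings are tempting and do not hold:
- A reader might infer that the trial is underpowered, or that a corrected figure would probably be worse. The documents give no correlation, and plausible values fall on both sides of 85%.
- A reader might take 2.1 as the SD of one rating. The text says only that it is the SD of baseline pain and does not say how many ratings lie behind it. The post-dose value averages three ratings, which may have a smaller SD.
- A reader might expect a null pain result to be taken as evidence against the mechanism at a known power. Nothing in the documents says so; section 2.2 places this study ahead of large-scale efficacy trials.

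**Conclusion.** The point holds in a limited form. The effect size is scaled by the across-patient SD of baseline pain, while the planned test depends on the SD of the between-session difference in change, which is not given. The 85% is therefore unsupported, in a direction that cannot be determined.

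The size rests on the assumed 1.1-point difference, an SD of 2.1 for every rating, two-sided 0.05 and 28 complete pairs. Across the correlations shown, power is 62% to 93% for post-dose pain and 47% to 95% for change scores. The 75.6% that follows from the printed inputs belongs to the one-sided/two-sided mismatch and should not be added to this point as a second loss. The division itself is correct; the fault is a missing input. It deserves correction because no other justification for 28 patients is offered, although the outcome concerned is secondary.

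**What to change.** Rewrite the sample-size paragraph of section 2.4.7 in four respects:
1. State the SD of the within-patient, between-session difference in change from baseline and its source. The group's own repeated pain data would serve if they contain suitable paired sessions; otherwise state the assumed rw and rd explicitly.
2. Recompute two-sided power for 28 pairs from that SD and label the effect size as the paired one.
3. Replace the single 85% with power over a plausible range of that SD or of the correlations, as in the tables above.
4. Resolve the one-sided/two-sided mismatch in the same edit, so that the gap from 85% to 76% is explained once.

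The cost is a wording change and a short calculation. Enrolment stays at 28, and neither the outcome nor the analysis changes. The stated power becomes a range that may lie above or below the present figure.

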3.0 Management of Intercurrent Events

3.1 Adverse Experiences

The investigators will closely monitor subjects for evidence of systemic adverse events. All adverse events will be reported and followed until satisfactory resolution. The description of the adverse experience will include the time of onset, duration, severity, etiology, relationship to the study drug (none, unlikely, possible, probable, highly probable), and any treatment required. Participants will notify the monitoring physician/RN coordinator of any adverse experience during the study period.

At discharge, subjects will be provided with contact information for team members and instructed to call if any adverse events occur.

3.2 Dose Limiting Toxicities

The dose-limiting toxicities (DLT) for the study are defined as follows:

- New QTc prolongation >60ms greater than baseline, or QTc>450ms
- Troponin T elevation > 0.03 ng/mL
- Syncope
- Sustained increase or decrease in SBP of >30 mmHg systolic or >20 mmHg diastolic
- Sustained vital sign abnormalities
 - HR<40 or >120 beats per minute
 - SpO2 <92%

- ALT/AST \geq 3xULN AND total bilirubin \geq 2xULN
- AST/ALT \geq 8xULN
- Altered mental status (delirium, inability to follow simple commands)
- Persistent visual disturbances

If DLT is observed in >2 participants, ondansetron dose will be reduced to 12 mg for all new participants.

If further DLT is observed in >2 participants receiving 12 mg ondansetron, the dose will be reduced to 8 mg for all new participants.

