3.3 Premature withdrawal from a study for a single patient

If at any time the constraints of this protocol are considered to be detrimental to the patient's health and/or the patient no longer wishes to continue protocol therapy, the participant will be withdrawn from the study and the reason(s) for withdrawal documented in the case report forms.

Any participant will be withdrawn from the study in the following scenarios:

- Death
- Anaphylaxis
- Allergic reaction with urticarial, rash or dyspnea,
- Cardiac arrest
- Atrial or ventricular fibrillation
- Ventricular Tachycardia
- Syncope
- AV block (2nd degree type II or 3rd degree)
- New QTc prolongation >60ms greater than baseline or >470ms for men or >480ms for women
- Troponin elevation > 0.03 ng/mL
- Sustained increase or decrease in SBP of >30 mmHg systolic or >20 mmHg diastolic
- Sustained vital sign abnormalities
 - HR<40 or >120 beats per minute
 - SpO₂ <92%
 - Temperature <36 C or >38°C
- ALT/AST \geq 3xULN AND total bilirubin \geq 2xULN
- AST/ALT \geq 8xULN
- Thrombocytopenia
- Clinically meaningful CBC abnormalities (compared to baseline)
- Altered mental status (delirium, inability to follow simple commands)
- Seizures
- Persistent visual disturbances
- General or specific changes in the patient's condition that render the patient unable to receive further treatment in the judgment of the investigator
- Suspected or confirmed pregnancy
- Serious non-compliance with the study protocol
- Lost to follow-up
- Patient withdraws consent
- Investigator removes the patient from study
- Investigator decides to close the study

If a participant withdraws from the study, the participant will be replaced in order to provide the required number of evaluable subjects. Subjects will be withdrawn if the investigator decides that discontinuation is in the best interest of the subject, or the subject requests withdrawal from the study.

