3.4 Adverse experiences and premature termination of the study

If any patient should suffer any serious adverse effect, including but not limited to serious neurologic or cardiovascular dysfunction or a reaction concerning for anaphylactic or anaphylactoid reaction, patient recruitment and randomization will be halted until the etiology of such an adverse reaction can be determined.

If two or more participants suffer any serious adverse effect, the study team will discuss premature termination of the study with Washington University IRB and the FDA.

If more than 7 participants meet the early withdrawal criteria, due to serious or non-serious adverse effects, the study will meet the early stopping criteria.

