3.6.1 Prevention, diagnosis and management of ondansetron-associated arrhythmia

To minimize the risk of ondansetron-associated arrhythmia, subjects will have a 12-lead ECG performed at the screening visit. Subjects with QTc>450msec or any arrhythmia will be excluded. Potential subjects that would be at elevated risk of developing ondansetron-associated arrhythmia (e.g., current use of QT-prolonging medication) are ineligible for this study. The ondansetron dose used (16mg IV infused over 15min) is approved and commonly used with chemotherapy. Subjects will be monitored with telemetry from the beginning of drug infusion until 2 hrs after infusion is complete. If arrhythmias or prolonged QT develop at any time during the study, subjects will be immediately assessed by a physician. If ECG abnormalities are mild (e.g., infrequent premature atrial/ventricular contractions or QTc>450ms but <500ms), subjects will be monitored in the pain management center by nursing and medical personnel for at least 4 hrs. If the signs/symptoms meet the severity criteria described in Section 3.2 ("Premature discontinuation of protocol for a single patient"), the patient will be withdrawn from the study and sent to the Barnes-Jewish Hospital emergency department (ED) for further evaluation, including cardiology consultation or hospital admission, as needed.

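### The closed DLT list in section 3.2 omits major arrhythmias that section 3.3 makes mandatory withdrawals, so a case without a listed sign does not count towards lowering the ondansetron dose

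*Combined protocol and SAP*

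**What the plan says.** Section 3.2 defines the DLTs by enumeration: QTc, troponin T, syncope, sustained blood-pressure change, sustained heart rate below 40 or above 120, sustained SpO2 below 92%, two liver criteria, altered mental status and persistent visual disturbance. There is no catch-all and no investigator-judgement item. The ECG entry is "New QTc prolongation >60ms greater than baseline, or QTc>450ms". The dose rule follows: "If DLT is observed in >2 participants, ondansetron dose will be reduced to 12 mg for all new participants". A second step, from 12 to 8 mg, uses the same list. The synopsis refers to 3.2 for dose reduction and adds no other trigger.

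Section 3.3 lists events for which any participant must be withdrawn. It includes "Atrial or ventricular fibrillation", ventricular tachycardia, cardiac arrest and "AV block (2nd degree type II or 3rd degree".

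Section 3.6.1 covers arrhythmia management. Its lower tier begins "If ECG abnormalities are mild (e.g., infrequent premature atrial/ventricular contractions or QTc>450ms but <500ms", and these participants are observed on site. In the upper tier "the patient will be withdrawn from the study and sent to the Barnes-Jewish Hospital emergency department (ED) for further evaluation". It also states: "Subjects will be monitored with telemetry from the beginning of drug infusion until 2 hrs after infusion is complete".

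Under section 3.4, after any serious adverse effect "patient recruitment and randomization will be halted until the etiology of such an adverse reaction can be determined". Two or more such cases lead to discussion of termination with the IRB and FDA, and more than 7 participants meeting withdrawal criteria meets the stopping rule. In section 3.7 the DSMB reviews serious or unexpected adverse events.

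**The concern.** The DLT count is the only stated automatic route to a lower dose for later participants. Every item in 3.2 reappears in 3.3 (with different QTc limits), but the rhythm items of 3.3 are not carried back to 3.2, and no reason is given. The count can therefore respond to a mild ECG finding and ignore a worse one.

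Suppose two DLTs have been counted at 16 mg. If a third participant has an isolated QTc of 451 ms, new participants move to 12 mg. If instead the third has a short VT run with no listed sign, that person is withdrawn and sent to the emergency department, and the count stays at two. New participants continue at 16 mg unless review of the event as serious or unexpected leads to a different decision. Section 3.5.4 describes QTc prolongation with possible progression to torsades as dose-dependent, so a ventricular arrhythmia is the kind of event a dose rule should register.

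**Working it through.** **Step 1: the two lists compared**

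| Event | 3.3 withdrawal | 3.2 DLT | Counted only through |
|---|---|---|---|
| Cardiac arrest | yes | no | syncope, HR, BP, SpO2, troponin, mental status |
| Ventricular fibrillation | yes | no | same |
| Ventricular tachycardia | yes | no | same, if sustained or symptomatic |
| Atrial fibrillation | yes | no | same, if sustained or symptomatic |
| High-grade AV block | yes | no | same, if sustained or symptomatic |
| Isolated QTc 451 ms | no (limits are >470 ms for men, >480 ms for women, or a rise >60 ms) | yes | direct |

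Cardiac arrest and ventricular fibrillation would nearly always produce a listed sign. What escapes is mainly a brief VT run, brief or rate-controlled AF, or asymptomatic high-grade block with a heart rate between 40 and 120. Telemetry can detect these, but 3.2 gives the finding no role.

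**Step 2: inputs for size**

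The plan states no operating characteristic for the rule, so there is no figure to reproduce.

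- Trigger: more than 2 participants, so 3 or more (3.2).
- Participants: 28 (2.4.7). The third event must fall by participant 27 for anyone to be left to dose.
- Listed-DLT rate p: not given; assumed 3-10%.
- Rate e of arrhythmias with no listed sign: not given; assumed 0.1%, with 1% as an upper bound. Section 3.5.4 puts all cardiac arrhythmias on ondansetron below 1%. Its 0 of 15 participants at 16 mg does not fix the rate, since the one-sided 95% upper bound is 1 - 0.05^(1/15) = 18%.
- The two event types are taken as disjoint, so the rate after the fix is p + e.

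**Step 3: chance of reaching 12 mg**

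P = 1 - Σ(k=0 to 2) C(27,k) p^k (1-p)^(27-k).

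At p = 5%: 1 - (0.2503 + 0.3558 + 0.2434) = 0.1505. At 5.1%: 1 - (0.2433 + 0.3531 + 0.2467) = 0.1569.

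| Listed-DLT rate | Now | e = 0.1% (gain in points) | e = 1% (gain in points) |
|---|---|---|---|
| 3% | 4.62% | 5.01% (0.39) | 9.18% (4.56) |
| 5% | 15.05% | 15.69% (0.65) | 21.86% (6.81) |
| 8% | 36.82% | 37.58% (0.76) | 44.33% (7.51) |
| 10% | 51.54% | 52.24% (0.70) | 58.29% (6.75) |

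Gains are taken before rounding.

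**Step 4: participants affected**

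The expected number dosed after the third event is Σ(k=3 to 27) C(k-1,2) p³ (1-p)^(k-3) (28-k). The increase when p becomes p + e is:

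| Listed-DLT rate | e = 0.1% | e = 1% |
|---|---|---|
| 3% | 0.03 | 0.38 |
| 5% | 0.06 | 0.65 |
| 8% | 0.09 | 0.88 |
| 10% | 0.09 | 0.92 |

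This assumes each outcome is known before the next participant starts. Sessions are 3 weeks apart, so enrolment may overlap. If three participants are already under way when the third event occurs, replacing (28-k) by max(0, 25-k) cuts the gain at 0.1% to about 0.02-0.07.

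The chance of at least one such arrhythmia among 28 is 1 - 0.999^28 = 2.8% at 0.1%, and 1 - 0.99^28 = 24.5% at 1%.

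**The case against.** The strongest reply is that the lists are tiered by design. Death, anaphylaxis and seizures are also in 3.3 and absent from 3.2. The most acute events go to 3.4, where a single serious effect halts recruitment, which is stricter than a three-participant count followed by a 4 mg reduction. On this view a low QTc threshold is sensible as an early, dose-related signal, and the mild label in 3.6.1 concerns bedside management rather than dose. Screening also removes non-sinus rhythm, QTc above 450 ms, heart failure and QT-prolonging drugs.

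Much of this stands. It limits the gap to events not judged serious, and the documents do not define serious. The DSMB also sees unexpected events, and nothing bars a dose change after review. But neither 3.4 nor 3.7 states a dose consequence, and tiering does not explain why a non-serious VT run should count for less than a QTc of 451 ms.

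The reply also blocks a stronger reading. A reader might infer from 3.5.4 that every omitted rhythm is dose-related. The sentence there quantifies QTc prolongation, in a paragraph about torsades. It supports the ventricular arrhythmias; the documents do not show that AF or AV block depends on ondansetron dose.

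**Conclusion.** The omission is real and minor. It concerns the automatic dose rule only, and in practice mainly brief VT, brief AF or asymptomatic high-grade block. The expected shift is about 0.03-0.09 of 28 participants from 16 to 12 mg at an assumed 0.1% rate, up to about 0.9 at the assumed 1% bound, and less if enrolment overlaps. All the rates are assumptions. The textual finding does not depend on them.

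Two further readings are tempting and unsupported. One is that dosing would simply continue through a life-threatening arrhythmia: a serious event halts recruitment and goes to the DSMB. The other is that tolerability results would be incomplete: 2.4.5.1 and 3.1 collect adverse events, ECG and vital signs whatever the DLT status.

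**What to change.** Add one bullet to 3.2: cardiac arrest, ventricular fibrillation, ventricular tachycardia, new atrial fibrillation, or second-degree type II or third-degree AV block. If the sponsor prefers to leave AF or AV block out because a dose relation is not shown, a sentence saying so would serve. Leave the halt and etiology review in 3.4 unchanged. As an editorial matter, the pointer in 3.6.1 to section 3.2 should read 3.3, since the title it gives describes the withdrawal section.

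No new data are needed, because telemetry and 12-lead ECG are already in place. The cost is that 12 mg may be reached slightly sooner, leaving slightly fewer participants at 16 mg. An arrhythmia unrelated to ondansetron would also count, as unrelated events under the existing items already do.
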